9.8 Supplementary analyses and quality control

Confounding-by-indication and healthy vaccinee bias are critical methodological concerns in studies of influenza VE. (46). Confounding by indication would result in an underestimate of true effectiveness if individuals with comorbidities that increase the risk of the study outcome are more likely to get vaccinated. Healthy vaccinee bias occurs when healthy individuals are more likely to get vaccinated while the most frail and sick elderly with the highest risk of the study outcome are not vaccinated, especially at the end of life. In Table 8 below, we present the key possible confounders in studies of effectiveness and how they are likely to be associated with study exposures and outcomes.

Table 8. List of possible confounders in IVE studies

Possible Confounder	Influenza vaccination propensity	Influenza hospitalisation risk	All-Cause Mortality risk	Bias Direction for VE against	Bias direction for VE against

				influenza hospitalisation	all-cause mortality
Comorbidity	↑	↑	↑	Underestimate	Underestimate
High frailty	↓	↑	↑	Overestimate	Overestimate
Healthcare seeking	↑	↑	↓	Underestimate	Overestimate
Healthcare access	↑	↑	↓	Underestimate	Overestimate

The current state-of-the-art in observational vaccination effectiveness estimation is comprised mainly of two study approaches, the test-negative design and TTE. Both approaches seek to mitigate the impact of bias and confounding. Guilin and colleagues (47) evaluated the performance of the two approaches in the evaluation of Covid-19 VE estimation. In data with rich covariate information, they observed similar VE estimates from the two methods. In data with only a few covariates, the test-negative design tended to overestimate the VE, while the target trial emulation underestimated the VE.

To evaluate the potential for biases by healthcare-seeking behaviour or healthcare access, the TTE will be supplemented by a TND study. The TND study is only feasible in Denmark due to lack of test-negative results in Finland and Sweden. Moreover, supplementary analysis comprising of PERR, RDA, and Negative Control Outcomes Analyses will be conducted to allow for comparison and contextualisation of results. Moreover, to strengthen the robustness of findings, triangulation—integrating evidence from multiple analyses with different methodologies—can provide valuable insights into potential biases and enhance the interpretation of results.

Test-Negative Case Control design

The test-negative case-control (TNCC) study design is a variant of the case-control method specifically developed for evaluating VE. (48) Due to unavailability of test negatives data in Finland and Sweden, we will conduct a TNCC study on Danish data only. In this approach, cases are individuals who test positive for influenza, while controls are those who test negative. The TNCC design offers several methodological strengths. It reduces bias from healthcare-seeking behaviour, as both cases and controls sought care and allows for efficient VE estimation during the influenza season. However, the TNCC design also has important limitations. It assumes that influenza vaccine does not affect the risk of other, non-influenza respiratory infections. (48) The design may be subject to bias if cases and

controls differ in disease severity. (49) Moreover, as the use of electronic healthcare records, including register-based data, for identifying cases and controls might cause bias (e.g., misclassification), and active enrolment of study participants is ideal in the TNCC design. (50) However, this increases the cost of the TNCC studies and limits its practicality to estimate VE against rare outcomes. Since a core assumption of the TNCC design is similar healthcare seeking behaviour among those who get tested, there is potential for selection bias if testing practices vary by vaccination status or other patient characteristics.

In the Danish population of individuals who were PCR-tested for influenza during the 2024–2025 season, we will employ a TNCC design to estimate the vaccine effectiveness against influenza infections during the 2024–2025 influenza season. We will exclude negative tests within 7 days of a previous negative test and within 21 days of a subsequent positive test. All tests within 90 days of a previous positive test will be excluded as these likely represent the same episode. Individuals can contribute with a maximum of one negative PCR test, which will be selected at random.

Patients will be considered vaccinated if they received an influenza vaccine at least 14 days before the PCR sample date. Patients will be considered unvaccinated if they have not received the influenza vaccine on the PCR test date or if they have received the influenza vaccine within two weeks before the PCR test date.

Logistic regression models will be used to estimate the odds ratio (OR) with 95% CIs. Our main estimate of interest is the vaccine effectiveness defined by $(1-OR) \times 100\%$. The models will be adjusted for age, sex, region of residency and comorbidities. We will assess whether the frequency of testing differs between vaccinated and unvaccinated groups during the season, since differential testing could bias VE estimates. The testing frequency will be visualized in a plot stratified by month and vaccination status.

Prior event rate adjustment

A difference-in-differences approach in the form of prior event rate ratio (PERR) adjustment exists for evaluating healthy vaccinee bias for influenza outcomes. (51) The PERR method is built on the assumption that any differences in event rates unrelated to vaccination between vaccinated and unvaccinated individuals can be observed in the period before vaccination is available. This can be implemented using the pairwise version of PERR. (51)

The matching and censoring criteria from the main TTE analysis will be applied. As before, the day the seasonal vaccine dose was administered within each matched pair will serve as the index date for both individuals. For each individual within a matched pair, the pre-vaccination period will be the start of the 2024/2025 influenza season (1 October 2024) until the index date and the post-vaccination period will start on day 14 following the index date. We will identify individuals who ultimately receive a seasonal influenza vaccine (“future vaccinated”) and those who remain unvaccinated (“future unvaccinated”), evaluated at the end of the studied period or on the date of the outcome. Both groups will have the number of outcomes and the amount of person-time measured in the pre-vaccination period (to establish baseline event rates) and in the post-vaccination season (to assess post-vaccination event rates).

The outcome under study is influenza-related hospitalization. Given that influenza hospitalization may be less frequent at the start of the influenza season, we will assess whether sufficient events occur in the pre-vaccination period to produce stable estimates.

We will employ the pairwise version of PERR, which effectively compares the ratio of (current vs. pre-vaccinated) event rates in the vaccinated group to the ratio of (current vs. pre-vaccinated) event rates in the unvaccinated group. Formally:

$$PERR = \frac{\frac{Event\ Rate_{Vaccinated,current}}{Event\ Rate_{Vaccinated,pre-vaccinated}}}{\frac{Event\ Rate_{Unvaccinated,current}}{Event\ Rate_{Unvaccinated,pre-vaccinated}}}$$

This ratio-of-ratios approach aims to adjust for pre-existing differences between those who choose vaccination and those who do not.

We will use Poisson regression to estimate event rates during the pre-vaccination and current periods. We will report point estimates and 95% confidence intervals for the PERR-adjusted measure of VE (1-PERR). The precision of these estimates will depend on the number of events in the pre-vaccination period. With high vaccine uptake and the vaccination occurring early in the start of the influenza season, the pre-vaccination period may produce fewer events. PERR results will be interpreted carefully and considered alongside the main matched cohort analyses and other supplementary analysis.

Negative control outcomes (NCO)

To evaluate the possible residual confounding in analysis of influenza vaccine effectiveness, we will analyse the association between influenza vaccination and the following negative control outcomes (NCO) in our main study design: Lower back pain (ICD10: M543-M545), clavicle fracture (ICD10: S420), and diverticulitis (ICD: K57).

Analysing negative control outcomes is a way to assess residual confounding. (70) Negative control outcomes such as lower back pain, clavicle fracture, and diverticulitis are conditions biologically unrelated to both vaccination and influenza. Any association between influenza vaccination and these outcomes would suggest residual confounding e.g. by healthcare seeking behaviour which could bias VE estimates. If no associations are found, it supports the validity of the primary analysis. Significant associations would indicate confounding that requires further adjustment or caution in interpretation. This relies on the assumption that the association between influenza vaccination and the negative control outcome is subject to the same confounders as the association between influenza vaccination and the influenza outcomes. Including negative control outcomes strengthens the study's credibility.

The study population will mirror the primary VE analysis, consisting of individuals aged 65 years or older, and adults under 65 years at high-risk. Vaccinated and unvaccinated individuals will be matched and the start of follow-up for matched pairs will be set at 14 days post-vaccination, ensuring alignment with the primary analysis. The statistical analysis will be conducted in the same way as our main cohort analysis, but negative control outcomes (lower back pain, clavicle fracture, and diverticulitis) will be evaluated instead of the influenza-related outcomes.

The results will be presented as cumulative incidence curves with RD and VE estimates. If no significant associations are found between influenza vaccination and the selected NCOs, this will support the validity of the primary VE analysis and suggest minimal residual confounding. If significant associations are observed, this will indicate residual confounding (e.g., differences in healthcare-seeking behavior) and warrant further exploration or caution in interpreting VE estimates.

Regression discontinuity analysis

For vaccination policies with treatment assignment according to age, regression discontinuity analyses (RDA) can be used to estimate a local average treatment effect (LATE) among individuals whose vaccination status is shifted by an eligibility threshold. Thus, we can estimate the LATE among 60-69-year-olds by comparing the risk in 65-69-yr-olds to the risk in the 60-64-yr-olds. This will provide a valid causal estimate under the assumptions of a) similar baseline risk of the influenza outcome in the two age groups, and b) strict adherence to the age recommendations. If adherence is not strict, we can

use fuzzy regression discontinuity analysis which uses an instrumental variables approach, where the cut-off is an instrument for actual treatment uptake. (52)

While this method can yield robust causal insights under relatively few assumptions, it faces limitations related to sample size, adherence, and external validity. We will interpret RDA findings as part of our broader range of supplementary analyses, recognizing that they estimate a local average treatment effect for compliers in a narrow age interval that may not generalize to the whole population, and should be considered alongside the main cohort findings and other designs (e.g., TNCC, PERR). We will carefully evaluate the number of outcomes in this age range to ensure sufficient power. Even if RDA provides a rigorous causal estimate for the subset near 65, it may not reflect the effect in much older or younger individuals.

We will focus on individuals in an age band of 60-69 years, where the policy recommends seasonal influenza vaccination at age 65. We will extract data on vaccination status at the end of the study period or date of the outcome (yes/no), age (in years), and influenza-related hospitalizations for individuals aged 60-69. This subset ensures that the age threshold of 65 is central in the data, capturing individuals who are just below (60-64) and just above (65-69) the cutoff. Individuals below 65 who are at high-risk will be excluded since they were also offered vaccination. Influenza vaccination will be as assigned as the “treatment” variable. The “instrument” will be a binary indicator of whether an individual’s age is ≥ 65 (the vaccination policy cutoff). This instrument should, in theory, increase the probability of vaccination but is not assumed to directly affect health outcomes other than through vaccination.

The statistical analysis will be conducted using a fuzzy regression discontinuity model. The probability of being vaccinated can be estimated as a function of age relative to 65 (e.g., age - 65) and an indicator for crossing the 65-year threshold. The predicted probability of being vaccinated will then be used to estimate the effect on the outcome of interest (influenza-related hospitalisation). The package *rdrobust* in R can be used to conduct this analysis. We will also construct figures to visualize the discontinuity for outcome and for treatment.

The main assumption is that, aside from the jump in vaccination likelihood at age 65, individuals just below vs. just above 65 should be comparable in terms of health and risk factors. To check this, we will inspect covariate distributions around the cut-off. We also expect to observe a noticeable “jump” in vaccination rates at age 65. If we do not observe this jump, it may indicate that the vaccination policy recommendation has weak influence, and the instrument’s strength may be inadequate.

Testing frequency

Tracking the frequency of influenza testing among vaccinated and unvaccinated individuals during follow-up provides insights into residual healthcare utilization or access bias. Testing rates can be compared between the groups to identify discrepancies that could influence VE estimates. We will assess testing frequency among vaccinated and unvaccinated individuals and stratify by calendar month to evaluate whether they are consistent across both groups and months, or driven by specific factors (e.g., timing patterns in a situation of increased testing activity during high influenza season). Ideally, we want the testing frequency to be similar. The results will be presented as the number of tests per group and calendar month, in a table or a graph. These steps ensure that any observed associations between vaccination and outcomes are not unduly influenced.

Sensitivity analysis before full immunization

We will conduct a sensitivity analysis using the primary cohort design (TTE approach) to evaluate vaccine effectiveness (VE) with an alternative time zero. The objective is to determine whether there is a difference in the incidence of influenza hospitalizations when time zero is set at the day of vaccination (Day 0) versus the day of full immunization (Day 14). Accordingly, we will estimate VE for the period from Day 0 to Day 14, and from Day 0 until the end of follow-up, to assess any potential effect of early events on our vaccine effectiveness estimates.

Quality control

Quality control will be conducted indirectly to evaluate the validity of our main analyses by 1) making sure that the prevalence of the vaccination schedule and the number of study endpoints match national surveillance dashboards and reports, 2) descriptive and analytical results are compatible with our previous findings, and 3) using a Common Data Model (CDM), by which national register data are standardized to a common structure, format and terminology in order to allow the same statistical programming scripts to be used in each country. The use of a CDM with common statistical programming scripts will facilitate efficient use of resources and reproducibility of the statistical analyses. We will ensure the scientific quality of the work, by division of review tasks (including statistical code review) and responsibilities in a timely fashion and by adhering to the ENCePP Code of Conduct. We will perform matching quality diagnostics to assess the control of matched parameters.

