Denmark (21)	
 - Individuals over 65 - Persons with certain chronic diseases, including: 
 o Persons with chronic lung diseases o Persons with cardiovascular diseases (excluding isolated, well-regulated high blood pressure) o Persons with type 1 or type 2 diabetes o Persons with congenital or acquired immunodeficiency¹ o Persons with impaired respiration due to reduced muscle strength o Persons with chronic liver or kidney disease o Persons with other chronic diseases where the condition, according to the doctor's assessment, leads to an increased risk from Covid-19 or infection² - Persons with severe obesity (BMI > 35) - Persons with other serious diseases or conditions, where the condition, according to the doctor's assessment, poses a serious health risk from Covid-19 or influenza³ - Persons in the same household as individuals with congenital or acquired immunodeficiency, or children at increased risk of severe outcomes from Covid-19 or influenza - Pregnant women in the 2nd or 3rd trimester⁴ - Early retirees
Sweden (22)	
 - Persons 65 years and above, pregnant women, and persons with certain underlying diseases including: 
 o Persons with chronic lung diseases o Persons with cardiovascular diseases (excluding isolated, well-regulated high blood pressure)

	
 ○ Persons with type 1 or type 2 diabetes ○ Persons with congenital or acquired immunodeficiency¹ ○ Persons with impaired respiration due to reduced muscle strength ○ Persons with chronic liver or kidney disease ○ Persons with other chronic diseases where the condition, according to the doctor's assessment, leads to an increased risk from Covid-19 or infection² - Persons with severe obesity (BMI > 35) - Persons with other serious diseases or conditions, where the condition, according to the doctor's assessment, poses a serious health risk from Covid-19 or influenza³ - Persons in the same household as individuals with congenital or acquired immunodeficiency, or children at increased risk of severe outcomes from Covid-19 or influenza - Pregnant women in the 2nd or 3rd trimester⁴ - Health care workers

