Influenza-related death	Denmark	The Civil Registration System and the Danish Microbiology Database. Defined as (the date of) death within 30 days after PCR positive test for influenza.
	Finland	The Finnish Population Information System and the National Infectious Diseases Register. Defined as (the date of) death within 30 days after PCR positive test for influenza.
	Sweden	The Total Population Register, the Cause of Death Register, and the Swedish Patient Register and the Register on surveillance of notifiable communicable diseases (SmiNet). Defined as (the date of) death within 30 days after PCR positive test for influenza.

Furthermore, medically attended outcomes presented in Table 5 will be assessed.

Table 5. Medically attended influenza outcomes

Variable	Country	Data source and details
Influenza-like-illness	Denmark	The National Patient Register. Defined as ICD-10 diagnostic codes J09, J10 and J11 used as a primary or secondary diagnosis.
	Finland	National Care Register for Health Care. Defined as ICD-10 diagnostic codes J09, J10 and J11 used as a primary diagnosis.
	Sweden	The Swedish Patient Register. Defined as ICD-10 diagnostic codes J09, J10 and J11 used as a primary diagnosis.
Hospitalisation for acute respiratory infections (ARI) and severe acute respiratory infections (SARI)	Denmark	The National Patient Register. A hospitalised patient is a SARI patient who a) has been admitted to hospital during the study period and has not been discharged to their home or home equivalent, b) inpatient contact or at least 12 hours of contact, and c) a ARI/SARI relevant primary diagnosis code (ICD-10: J09-J22).
	Finland	National Care Register for Health Care and the National Infectious Diseases Register. A hospitalised patient is a SARI patient who a) has been admitted to hospital during the study period and has not been discharged to their home or home equivalent, b) inpatient contact or at least 12 hours of contact, and c) a ARI/SARI relevant primary diagnosis code (ICD-10: J09-J22)
	Sweden	The Swedish Patient Register and the Register on surveillance of notifiable communicable diseases (SmiNet). A hospitalised patient is a SARI patient who a) has been admitted to hospital during the study period and has not been discharged to their home or home equivalent, b) inpatient contact or at least 12 hours of contact, and c) a ARI/SARI relevant primary diagnosis code (ICD-10: J09-J22)

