The Danish Microbiology Database	Information on positive results of RT-PCR tests for influenza are obtained from The Danish Microbiology Database (MiBa) which holds information on all microbiology samples analysed at Danish departments of microbiology, including information on influenza test results, date of sampling, date of analysis, type of test and interpretation of the test (positive / negative).	Register	Nationwide	2020 – today	Daily	No lag	(27)

Country	Details of the individual-level data sources						
Finland							
Title	Info	Type	Setting	Study availability	Update	Lag	Ref
Finnish Population Information System	The register is held by the Digital and Population Data Services Agency and contains personal data on all permanent residents in Finland such as the unique personal identifier, date of birth, place of residence, date of death, and date of immigration, and emigration.	Register	Nationwide	1964 - today	Daily	No lag	(28)
National Vaccination Register	The register, which is based on the Register of Primary Health Care Visits, holds information on almost all influenza vaccinations administered in Finland; only influenza vaccinations given by social care givers such as nursing homes might be incompletely covered. Data include the date of vaccination, vaccine batch number and trade name.	Register	Nationwide	2009 - today	Daily	No lag	(29)

Care Register for Health Care	The register comprises information on all in-hospital care (since 1969) and outpatient specialist care (since 1998) in Finland, including admission and discharge dates, whether hospitalisation was planned or acute, codes for discharge diagnoses (according to ICD-10) and surgical procedures, whether discharged as deceased, to own private residence or other health care facilities, type of department and hospital. The register is held by the Finnish Institute for Health and Welfare.	Register	Nationwide	1967 - today	Daily	1-4 weeks	(30)
Register for Primary Health Care Visits	The register is held by Finnish Institute for Health and Welfare and holds data on all primary health care services delivered in Finland.	Register	Nationwide	2011 - today	Daily	No lag	(31)

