9.7 Data analysis

Procedures

We will use a matched cohort design to evaluate the effectiveness of seasonal influenza vaccine in comparison with not receiving a seasonal influenza vaccine. Individuals who have received the vaccine will be matched on the day of vaccination with individuals who have not yet received the vaccine. Individuals will be matched on age (5-year bins), sex, region of residence, and selected comorbidities. The day the seasonal vaccine dose was administered within each matched pair will serve as the index date for both individuals. If individuals who were included as a matched non-vaccinated individual

(i.e., a reference individual) receive a vaccine later than the assigned index date, the pair will be right-censored on the day the non-vaccinated individual is vaccinated. In these cases, the non-vaccinated individuals will be allowed to potentially re-enter as vaccine recipients in a new matched pair on that given date.

Statistical analysis

We will follow individuals from day 14 after the index date (to ensure full immunisation) up until the day of an outcome event, death, emigration, or end of the study, whichever occurs first. Additionally, we will censor individuals with a positive PCR test for influenza in our follow-up period 14 and 30 days after the test (as a positive test will be part of the outcome definitions) for the influenza hospitalisation and death outcome analyses, respectively. We will right-censor matched pairs when the reference unvaccinated individual receives a vaccine during follow-up. Cumulative incidences will be estimated by the Aalen-Johansen estimator, and from these we will calculate the comparative VE as $1 - \text{risk ratio}$ at the start of week 18 (depending on data availability) since index date. The corresponding 95% CI will be calculated using the delta method. Country-specific estimates will be combined by random-effects meta-analyses implemented using the *mixmeta* package in R.

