12. PLANS FOR DISSEMINATING AND COMMUNICATING STUDY RESULTS

Main results expected in the final study report:

- Baseline characteristics tables, including prior to matching and after matching, of two separate cohorts of 65+-year-olds (trial 1) and 18-64 years-of-age at increased risk (trial 2)
- Figures of cumulative incidence curves for vaccinated and unvaccinated, per country, outcome, brand and trial
- Brand-specific effectiveness estimates-tables with stratified analyses (age, sex, comorbidity, Covid-19 status, influenza vaccination history)
- Supplementary analyses results

We anticipate one manuscript, and findings will be reported to the general public by institutional press releases upon acceptance in academic peer-review journals or upon uploading to a pre-print server (if decided relevant to do so). The study protocol and study report deliverables will be made public in the HMA-EMA Catalogue of RWD studies when approved by EMA. We will adhere to the STROBE and ENCePP guidelines for the conduct of observational studies and for scientific independence and transparency.

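### The Danish test-negative analysis keeps SARS-CoV-2-positive people as controls and leaves out COVID-19 vaccination, which would pull its VE estimate down if uptake of the two vaccines is linked

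*Protocol*

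**What the plan says.** Section 9.8 (Test-Negative Case Control design) takes Danish residents PCR-tested for influenza, and "cases are individuals who test positive for influenza, while controls are those who test negative". Tests are dropped only for closeness to an earlier negative, a later positive or an earlier positive test, and each person gives at most one negative test. Nothing refers to SARS-CoV-2. For the logistic regression, "The models will be adjusted for age, sex, region of residency and comorbidities". Of the design's assumptions, the protocol states: "It assumes that influenza vaccine does not affect the risk of other, non-influenza respiratory infections".

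The cohort uses the same kind of covariates (section 9.7): "Individuals will be matched on age (5-year bins), sex, region of residence, and selected comorbidities". COVID-19 vaccination is not in Table 6 (covariates), Table 8 (possible confounders) or the stratification list in section 9.3.

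Covid-19 does appear in two relevant places. Table 2, for Denmark and Sweden, includes household contacts of "children at increased risk of severe outcomes from Covid-19 or influenza" and uses similar joint wording for other risk groups. Section 12 promises "Brand-specific effectiveness estimates-tables with stratified analyses (age, sex, comorbidity, Covid-19 status, influenza vaccination history"), without saying whether the Covid-19 item means infection or vaccination.

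Two secondary cohort outcomes need no influenza test: all-cause mortality, and ARI/SARI admission, defined by "a ARI/SARI relevant primary diagnosis code (ICD-10: J09-J22").

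**The concern.** A test-negative design estimates VE correctly only if controls show the vaccination odds of the population that gave rise to the cases. The protocol states this for a direct effect of the influenza vaccine on other infections. A second vaccine that is taken by the same people and prevents one of the control illnesses does the same damage. People who reach the control group because of COVID-19 are then less often COVID-19 vaccinated and, through the correlation, less often influenza vaccinated. Control vaccination odds fall, the odds ratio rises and VE falls.

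Section 9.8 introduces this analysis to evaluate bias from healthcare seeking and access in the cohort. Table 8 expects that bias to make the cohort underestimate VE against influenza hospitalisation, so its signature would be a test-negative VE above the cohort VE. A downward shift in the test-negative VE can hide that signal or be mistaken for a different bias.

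Separately, a COVID-19 vaccine that prevents deaths or respiratory admissions would make the influenza vaccine look better on outcomes that do not require influenza. The planned negative control outcomes (lower back pain, clavicle fracture, diverticulitis) would not show this, because COVID-19 vaccination does not plausibly affect them.

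**Working it through.** The protocol gives no size, precision or bias figure for the test-negative analysis, so there is nothing to reproduce. The size below rests on assumptions.

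**Test-negative analysis**

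Assumptions, none in the documents:
- COVID-19 vaccine uptake is c1 = 85-90% in influenza vaccinees and c0 = 5-10% in others.
- COVID-19 vaccine effectiveness is VEc = 30-50%.
- 70% of the other controls are influenza vaccinated, so their odds are o = 0.7/0.3 = 2.333.
- True influenza VE is 40%.
- s is the share of controls who are SARS-CoV-2 positive.

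Formulas:
1. Influenza vaccination odds in SARS-CoV-2-positive controls = o × (1 − c1·VEc)/(1 − c0·VEc).
2. Convert to a proportion, mix with 70% using weights s and 1 − s, and convert back to odds o_mix.
3. Observed VE = 1 − 0.60 × o/o_mix.

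Upper end (c1 = 0.90, c0 = 0.05, VEc = 0.50): the ratio is 0.55/0.975 = 0.564, the odds are 1.316 and the proportion is 0.568. At s = 0.20, the mixed proportion is 0.8 × 0.70 + 0.2 × 0.568 = 0.674. Then o_mix = 2.064 and VE = 1 − 1.4/2.064 = 32.2%.

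Lower end (c1 = 0.85, c0 = 0.10, VEc = 0.30): the ratio is 0.745/0.97 = 0.768 and the proportion is 0.642. At s = 0.05, o_mix = 2.301 and VE = 39.2%.

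| SARS-CoV-2-positive share of controls | Observed VE (true 40%) | Loss, points |
|---|---|---|
| 5% | 38.1-39.2% | 0.8-1.9 |
| 10% | 36.2-38.3% | 1.7-3.8 |
| 20% | 32.2-36.6% | 3.4-7.8 |

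**Wider uptake range.** A second formula is VE = 1 − (1 − 0.40)/R, with R = (1 − s·e·a)/(1 − s·e·b). Here a and b are uptake in influenza vaccinees and others, e is COVID-19 VE, and s is now the SARS-CoV-2-positive share among COVID-19-unvaccinated controls.
- With a = 60-90%, b = 5-20%, s = 5-30% and e = 30-50%, the loss runs from 0.4 to 8.8 points.
- With the mildest contrast (60% vs 20%) and s of 5-15%, it is 0.4-1.9 points.
- With a = b it is zero.

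**Simulation.** This used 4 million people, the Danish 65+ coverage of 75.6% from section 9.5, true VE 40%, a = 0.8, b = 0.1, s = 15% and e = 50%. The formula predicts 1 − 0.60/(0.94/0.9925) = 36.6%.
- As planned: 36.6% (95% CI 35.2-38.0).
- SARS-CoV-2-positive controls excluded: 39.7% (38.3-41.0).
- COVID-19 vaccination added to the model instead: 38.9% (37.1-40.7).

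**Secondary cohort outcomes**

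Assume no true influenza vaccine effect, and let s be the share of events due to COVID-19 in the influenza-unvaccinated. Spurious VE = s × [1 − (1 − 0.85·VEc)/(1 − 0.10·VEc)]. The bracket is 0.232 at VEc = 30% and 0.395 at 50%. Spurious VE is therefore 1-2% at s = 5%, 2-4% at 10% and 5-8% at 20%.

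**The case against.** The strongest reply is that little of importance is touched, and much of it stands.

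- **Primary outcomes.** A reader might infer that the study's main VE estimates are biased. They are not biased by this route, because every primary outcome requires a positive influenza test. The test-negative analysis is supplementary and Denmark-only, and ARI/SARI and all-cause mortality are secondary.
- **Two biases in opposite directions.** A reader might infer that the test-negative VE is pushed down while the cohort VE is pushed up, widening the gap from both sides. The documents do not support this. The test-negative analysis targets influenza infection, so its cohort counterpart is laboratory-confirmed influenza. Only the test-negative side moves.
- **Evidence of co-vaccination.** This is indirect: joint risk-group wording for Denmark and Sweden, and the title of a cited Swedish notice covering both vaccines. The Finnish list in Table 2 does not mention Covid-19. No uptake figure is given, and 85-90% against 5-10% is a strong contrast. That limits the claim about size; it does not change the direction.
- **Precision.** The Danish test-negative study cited in section 7 had VE 35.0% with a CI of 11.1-52.4, so a shift of a few points could lie well inside the interval. That is true, but the bias does not shrink with more data.
- **Already acknowledged.** Section 7 warns that all-cause mortality can overestimate benefit, section 9.8 lists limitations of the test-negative design, and results are to be triangulated. None of this names COVID-19 vaccination or alters the control set. The undefined Covid-19 stratum in section 12 belongs to the brand-specific tables and changes neither the controls nor the model.
- **ARI/SARI.** The effect depends on how many COVID-19 admissions carry a J09-J22 primary code, which the protocol does not say. The point is conditional for that outcome; mortality has no such dependence.

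**Conclusion.** The point holds for the Danish test-negative analysis. The protocol itself fixes the control definition, exclusions and covariates, so this is not detail left to a later plan. Given positively correlated uptake and any COVID-19 vaccine effect, VE is biased downward. Under the stated assumptions the loss is about 1-4 points with 5-10% SARS-CoV-2-positive controls and up to about 8 points at 20%. It vanishes if uptake is uncorrelated. The practical harm is to the comparison with the cohort's laboratory-confirmed influenza estimate.

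The secondary point is weaker. All-cause mortality, and ARI/SARI as far as coding allows, may absorb some COVID-19 vaccine benefit, by about 1-8% spurious VE over the assumed range.

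A reader might go further and ask for COVID-19 vaccination as a matching factor throughout. The documents do not support that. With 75.6% coverage in Danish residents aged 65+ and assumed uptake of 85% against 10%, about 0.756 × 0.85 = 64% would have both vaccines and 0.244 × 0.10 = 2.4% the COVID-19 vaccine alone. Most co-vaccinated people would have no lasting control, and the estimand, the average effect among the vaccinated, would change.

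**What to change.** 1. **Test-negative analysis (section 9.8).** Exclude control tests from people with a positive SARS-CoV-2 test on the same sample or within 14 days. Report the unrestricted control set as a sensitivity analysis. The Danish Microbiology Database, already the source of the influenza tests, "holds information on all microbiology samples analysed at Danish departments of microbiology". The cost is one exclusion rule and a small loss of controls.

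2. **Secondary cohort outcomes (sections 9.3 and 12).** Define Covid-19 status as receipt of a 2024-25 COVID-19 vaccine, assessed by the start of follow-up (day 14) so that no later information enters. Add it to the stratification list. Report a Danish sensitivity analysis by it for all-cause mortality and ARI/SARI, leaving the main estimand unchanged. The Danish vaccination register is described as covering all vaccinations. The Finnish and Swedish vaccination entries in Table 7 mention influenza vaccines only, so feasibility is shown for Denmark alone. The cost is some added code, and the COVID-19-vaccinated stratum will be imprecise because it will have few lasting controls.

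3. **Wording.** Beside the stated test-negative assumption, add that a correlated vaccine acting on control infections also violates it.
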